## 2 PROTOCOL SYNOPSIS

Study Title	Phase 2, Randomized, Double-Blind, Placebo-Controlled, Dose-Finding Study to Assess the Efficacy, Safety, Pharmacokinetics, and Pharmacodynamics of Vadadustat in Japanese Subjects with Anemia Secondary to Dialysis-Dependent Chronic Kidney Disease (DD-CKD)
Protocol Number	AKB-6548-CI-0022
Study Phase	Phase 2
Investigational Product	Vadadustat; each tablet contains 150 mg of vadadustat for oral administration
Study Population	The study population will consist of male and female Japanese adults aged 20 years or older with anemia secondary to DD-CKD
Investigative Sites	Approximately 35 sites in Japan
Planned Number of Subjects	
Approximately 48 subjects will be enrolled in the study, with 36 subjects receiving one of 3 doses of vadadustat and 12 subjects receiving placebo during the primary efficacy period:
 
 
• 150 mg vadadustat once daily (n=12)
 
• 300 mg vadadustat once daily (n=12)
 
• 600 mg vadadustat once daily (n=12)
 
• Placebo (n=12)
 

Study Objectives	
 
• Primary Objective: To assess the dose-response relationship between oral vadadustat once daily dosing for 6 weeks and the change in hemoglobin (Hb) in Japanese subjects with anemia secondary to DD-CKD; this is to define the starting dose for use in Phase 3 clinical studies in Japan
 
• Secondary Objectives: 
 
– To assess the safety, tolerability, pharmacokinetics (PK), and pharmacodynamics (PD) of oral vadadustat once daily dosing in Japanese subjects with anemia secondary to DD-CKD during the 6-week, primary efficacy period
 
– To evaluate the effect of dose adjustments and demonstrate the maintenance effect on Hb during a 10-week dose adjustment and maintenance period
 
– To assess the time to reach the target Hb level from baseline
 
 
 

Overview of Study Design	
This is a Phase 2, randomized, double-blind, placebo-controlled, dose-finding study to assess the efficacy, safety, tolerability, PK, and PD of orally administered vadadustat in Japanese subjects with anemia secondary to DD-CKD.
 
The study will include the following periods:
 
 
• Eligibility screening period (up to 11 weeks)
 
• Primary efficacy period (6 weeks; Weeks 1 to 6)
 
• Dose adjustment and maintenance period (10 weeks; Weeks 7 to 16)
 
• Follow-up period (2 weeks; Weeks 17 and 18)
 
 
During the screening period, subjects who have recently received ESA therapy and otherwise meet eligibility criteria will be required to washout from ESA therapy prior to evaluation of screening Hb (see “Inclusion Criteria” below).
 
Following the screening period, eligible subjects will be randomized to receive blinded study drug, either vadadustat (150, 300, or 600 mg vadadustat) or placebo. See “Dosage and Regimen” below for additional information regarding the randomization scheme.

	
Fixed-dose treatment during the primary efficacy period will allow a dose-response relationship to be established. No increase in study drug dose is permitted during this period. However, if Hb level increases rapidly or if the Hb level exceeds 13.0g/dL the study drug dose can be decreased or interrupted following the dose adjustment guidelines listed under “Dosage and Regimen” (see below).
 
After completing the primary efficacy period, subjects will continue to a 10-week dose adjustment and maintenance period. Subjects receiving placebo will be switched to vadadustat, and study drug dose will be adjusted to achieve a target Hb of 10.0-12.0 g/dL based on dose adjustment guidelines (see “Dosage and Regimen,” below).
 
Study drug will be discontinued after the dose adjustment and maintenance period has been completed (Week 16) and subjects will continue to a 2-week follow-up period (Week 17-18).


Study Duration
	
Study duration will depend on ESA use as follows:
 
 
• For subjects who were not prescribed ESAs prior to study entry: Up to 22 weeks, including the eligibility screening period (up to 4 weeks, with 2 screening visits), primary efficacy period (6 weeks), dose adjustment and maintenance period (10 weeks), and follow-up period (2 weeks)
 
• For subjects who were prescribed ESAs prior to study entry: Up to 29 weeks, including the eligibility screening period (up to 11 weeks, with 3 screening visits), primary efficacy period (6 weeks), dose adjustment and maintenance period (10 weeks), and follow-up period (2 weeks)
 
 
Note: Subjects who discontinue prematurely from the study or permanently discontinue study medication will complete the end-of-treatment (Week 16) visit followed in two weeks by the Week 18 visit.


Key Inclusion Criteria (the complete list is provided in the protocol)
	
 
• Male and female Japanese subjects (20 years or older)
 
• Receiving chronic maintenance hemodialysis for end-stage kidney disease for at least 8 weeks prior to screening
 
• ESA status and screening Hb that meet one of the following criteria:             
 
– For subjects who are not being treated with ESAs: Mean Hb <10.0 g/dL; average of 2 measurements obtained during screening. These subjects must be off ESAs for at least the following periods of time prior to screening visit 1:                 
 
• 2 weeks for epoetin alfa, epoetin beta, or epoetin kappa;
 
• 4 weeks for darbepoetin alfa;
 
• 8 weeks for epoetin beta pegol.
 
 
 
– For subjects who are being treated with ESAs: Mean Hb <10.0 g/dL; average of 2 measurements obtained during screening after the protocol-defined ESA washout period. These subjects must washout ESA therapy for the following periods of time during the screening period, beginning at screening visit 1 and prior to screening visit 2:                 
 
• 2 weeks for epoetin alfa, epoetin beta, and epoetin kappa;
 
• 4 weeks for darbepoetin alfa;
 
• 8 weeks for epoetin beta pegol.
 
 
 
 
 
• Serum ferritin <math>\geq</math>50 ng/mL during screening
 
• Transferrin saturation (TSAT) <math>\geq</math>20% during screening
 
• Folate and vitamin B12 <math>\geq</math>lower limit of normal during screening
 
• For subjects who are receiving oral or intravenous iron supplementation, the dose of iron supplementation must be stable for at least 28 days prior to the screening period. For subjects who are not receiving oral or intravenous iron supplementation, no iron supplementation may have been administered for at least 28 days prior to the screening
 

	period.
Key Exclusion Criteria (the complete list is provided in the protocol)	Anemia due to a cause other than CKD or presence of active bleeding or recent blood loss; sickle cell disease, myelodysplastic syndromes, bone marrow fibrosis, hematologic malignancy, myeloma, hemolytic anemia, thalassemia, or pure red cell aplasia; red blood cell (RBC) transfusion within 4 weeks prior to or during screening; anticipated to recover adequate kidney function to no longer require hemodialysis during study participation; on peritoneal dialysis or expected to change dialysis modality during study participation; and hypo-responsiveness to ESA defined as any of the following ESA treatments within 8 weeks prior to screening: (i) intravenous epoetin dose $\geq 3000$ units/dose 3 times a week (9000 units/week), (ii) intravenous darbepoetin alfa dose $\geq 60$ $\mu\text{g}$ once a week, or (iii) epoetin beta pegol $\geq 200$ $\mu\text{g}$ once a month or $\geq 100$ $\mu\text{g}$ once every 2 weeks
Retesting/Rescreening	
Subjects who initially fail to qualify for the study based on laboratory test results may be retested once within the screening period, at the investigator's discretion.
 
Subjects who fail to meet the qualifying criteria for Hb during screening may be considered for rescreening at the discretion of the investigator, if it is felt that the subject's status has changed and that the subject may now qualify for the study. Additionally, subjects who fail to qualify for the study based on low ferritin, TSAT, folate, or vitamin B12 values may be considered for rescreening after receiving replacement therapy.
 
Screening is limited to 3 attempts (initial screening and 2 additional rescreening attempts).

Efficacy and Pharmacokinetic Endpoints	
Note that a pre-treatment average value for Hb is defined as the average of 3 values obtained prior to dosing, ie, the 2 qualifying screening values and the baseline value.
 
Primary Endpoint:
 
 
• Mean change in Hb levels from pre-treatment to the end of the primary efficacy period (Week 6)
 
 
Secondary Endpoints:
 
 
• Time to reach target Hb level of 10.0-12.0 g/dL from baseline
 
• Mean Hb levels at the end of the primary efficacy period (Week 6) and the end of the dose adjustment and maintenance period (Week 16)
 
• Proportion of subjects who achieve target Hb 10-12 g/dL at the end of the dose adjustment and maintenance period (Week 16)
 
• Mean change in Hb between pre-treatment and the end of the dose adjustment and maintenance period (Week 16)
 
• Mean change in hematocrit, RBC count, and reticulocyte count from baseline to the end of the primary efficacy period (Week 6) and the end of the dose adjustment and maintenance period (Week 16)
 
• Mean change in iron indices (ie, iron, total iron-binding capacity [TIBC], TSAT, and ferritin) and hepcidin from baseline to the end of the primary efficacy period (Week 6) and the end of the dose adjustment and maintenance period (Week 16)
 
• Proportion of subjects requiring rescue with RBC transfusion from baseline to the end of the primary efficacy period (Week 6) and the end of the dose adjustment and maintenance period (Week 16)
 
• Proportion of subjects requiring rescue with ESAs from baseline to the end of the primary efficacy period (Week 6) and the end of the dose adjustment and maintenance period (Week 16)
 
• Number of dose adjustments from baseline to the end of the dose adjustment and maintenance period (Week 16)
 
• Plasma concentration profile of vadadustat and its metabolites using pre-dose sample from Week 4
 

Safety Endpoints
	
Safety assessments, including adverse events, vital signs, electrocardiograms (ECGs), and other laboratory assay results (eg, chemistry, components of the complete blood count [CBC] other than the ones noted above, and vascular endothelial growth factor [VEGF])


Dosage and Regimen
	
Study drug will be administered on an outpatient basis. Subjects should take the study medication with water or another beverage and should be instructed to swallow the intact tablet(s). Subjects may take the study medication with or without food.
 
Primary efficacy period (Day 1 to Week 6)
 
Using a central randomization system, subjects will be randomized at a 1:1:1 ratio to receive 1 tablet (150 mg vadadustat or placebo), 2 tablets (300 mg vadadustat or placebo), or 4 tablets (600 mg vadadustat or placebo) of study drug. Within each tablet-count group, subjects will be randomized 3:1 to receive vadadustat or placebo as shown below.
 
Figure. Treatment Randomization Scheme
  <pre> graph LR     A[1 tablet (n=16)] --> B[Vadadustat 150 mg (n=12); 1 x 150 mg tablet once daily]     A --> C[Placebo (n=4); 1 tablet once daily]     D[2 tablets (n=16)] --> E[Vadadustat 300 mg (n=12); 2 x 150 mg tablets once daily]     D --> F[Placebo (n=4); 2 tablets once daily]     G[4 tablets (n=16)] --> H[Vadadustat 600 mg (n=12); 4 x 150 mg tablets once daily]     G --> I[Placebo (n=4); 4 tablets once daily]     </pre> 
The primary efficacy period involves fixed-dose treatment to establish a dose-response relationship. No increase in study drug dose is permitted during this period. However, the dose may be decreased or interrupted as described below.
 
 
• If the Hb increases rapidly (eg, more than 1 g/dL in any 2-week period), reduce the dose by 1 tablet.
 
• If the Hb exceeds 13.0 g/dL, interrupt study drug until the Hb decreases to 12.5 g/dL or below and then resume dosing with 1 fewer tablet.
 
 
If dose reduction or interruption is recommended based on the central laboratory Hb result and protocol-specified guidelines, the investigative site will contact the subject within 1 business day of receiving the Hb result from the central laboratory. If possible, the subject will be scheduled for an additional visit within 3 business days. If scheduling the subject within this time frame is not possible, dosing instructions will be provided to the subject over the telephone.
 
Dose adjustment and maintenance period (Weeks 7 to 16):
 
Subjects who complete the primary efficacy period will enter the dose adjustment and maintenance period. Subjects receiving placebo will be switched to vadadustat. Dose adjustments for study drug will follow the dose adjustment guidelines listed below to achieve a target Hb of 10.0-12.0 g/dL. Dose adjustments will be based on central laboratory Hb results from study visits at Weeks 6, 8, 10, 12, and 14.
 
 
• Do not increase the dose more frequently than once within any given 4-week interval. For example, if a subject's dose was increased based on Hb results from the Week 6 visit and the subject remains below the Hb target, the next opportunity to further increase the dose would be based on Hb results from the Week 10 visit. Decreases in dose can occur more frequently. Avoid frequent dose adjustments.
 
• If the Hb has not increased by more than 0.5 g/dL above the baseline value after the
 


	
first 6 weeks of treatment, increase the dose by 1 tablet.
 
 
• Increase the dose by 1 tablet every 4 weeks until Hb is above 10.0 g/dL (maximum dose is 4 tablets).
 
• If the Hb increases rapidly (eg, more than 1 g/dL in any 2-week period), reduce the dose by 1 tablet.
 
• If the Hb falls below 10.0 g/dL, increase the dose by 1 tablet.
 
• If the Hb exceeds 12.0 g/dL, reduce the dose by 1 tablet.
 
• If the Hb exceeds 13.0 g/dL, interrupt study drug until the Hb decreases to 12.5 g/dL or below and then resume dosing with 1 fewer tablet.
 
• If a dose adjustment is required to maintain Hb at the desired level, the dose adjustment is by 1 tablet.
 
 
If dose adjustment is recommended based on the central laboratory Hb result and protocol-specified guidelines, the investigative site will contact the subject within 1 business day of receiving the Hb result from the central laboratory. If possible, the subject will be scheduled for an additional visit within 3 business days to discuss the dosing change and to dispense additional study drug if necessary (for subjects who receive a dose increase). If scheduling the subject within this time frame is not possible, dosing instructions will be provided to the subject over the telephone.
 
Note: If subjects fail to achieve target Hb level despite administration of 4 tablets of study drug per day, this will not be considered a reason for subject discontinuation unless the subject initiates rescue therapy (see “Rescue Therapy Guidelines” below).


Rescue Therapy Guidelines
	
ESA Rescue Therapy
 
In order to standardize the use of ESA rescue in the study, the following guidelines should be followed. ESA rescue therapy may be considered if:
 
 
• ESA is considered warranted by the investigator’s judgment, AND
 
• The subject experiences a clinically significant worsening of anemia or symptoms of anemia, AND
 
• The subject has a confirmed Hb level <9.0 g/dL as defined by two consecutive Hb levels <9.0 g/dL. The investigator may schedule the subject to return for an unscheduled visit to confirm Hb level <9.0 g/dL prior to the subsequent scheduled study visit.
 
 
If clinically indicated, the investigator at his/her discretion may initiate ESA rescue therapy without a confirmatory Hb level <9.0 g/dL if the first two criteria above are met.
 
Red Blood Cell Transfusions
 
Investigators should use their local institution’s transfusion guidelines when determining whether to transfuse a study subject.
 
Subjects who initiate either rescue therapy, ESA Rescue Therapy or Red Blood Cell Transfusion, will be required to stop study drug treatment and will be discontinued from the study. See “Study Duration” for follow-up of subjects who discontinue early from the study.

Iron Supplementation
	
Subjects who are receiving a stable dose of oral or intravenous iron supplementation for at least 28 days prior to the screening period should continue their iron supplementation at the same dose and route of administration through the primary efficacy period (through Week 6). Changes to iron supplementation dose during the primary efficacy period will be considered protocol deviations but will not be considered a reason for subject discontinuation. After the Week 6 visit, investigators should prescribe iron supplementation as needed for subjects with ferritin <100 ng/mL and TSAT <20%, and the dose and route of iron administration will be

	
selected at the investigator’s discretion.
 
Subjects who are not receiving iron supplementation at the beginning of the screening period should not start iron supplementation through the primary efficacy period (through Week 6). Initiation of iron supplementation during the primary efficacy period will be considered a protocol deviation but will not be considered a reason for subject discontinuation. After the Week 6 visit, investigators should prescribe iron supplementation as needed for subjects with ferritin <100 ng/mL and TSAT <20%, and the dose and route of iron administration will be selected at the investigator’s discretion.
 
Important: Because of the potential for oral iron to reduce the bioavailability of vadadustat, study drug (vadadustat or placebo) should not be administered concurrently with any oral iron supplement. Any oral iron supplements (including multivitamins containing iron) should be taken at least 2 hours before or 2 hours after the dose of study drug.


Statistical Considerations
	
An analysis of covariance (ANCOVA) model will be used to compare change from pre-treatment in Hb between the 3 vadadustat dosing groups and the placebo group. The model will include treatment assignment (3 dosed groups and 1 placebo group) and pre-treatment Hb value as a covariate. A step-down procedure will be used to control the overall type I error rate for the multiple comparisons. Testing of the highest dose compared with placebo will be conducted first. If and only if this comparison is significant, then testing will proceed to comparison of the next lower dose and placebo, and so on. Thus, no multiplicity adjustment will be needed for this analysis.
 
The sample size and power calculations are based on results from Study AKB-6548-CI-0005 that was conducted in the United States and evaluated vadadustat in patients with anemia secondary to non-dialysis-dependent CKD. It is reasonable to extrapolate these data to the current study based on the following findings:
 
 
• PK parameters of vadadustat are similar between CKD patients who are receiving hemodialysis (Study AKB-6548-CI-0009) and CKD patients who are not receiving dialysis (Study AKB-6548-CI-0003)
 
• Hemodialysis procedure has no significant impact on the PK of vadadustat (Study AKB-6548-CI-0009)
 
• The dose range of 150-600 mg of vadadustat to be used in the current study has been shown to be generally well-tolerated and efficacious in raising and/or maintaining Hb at the desired target level in CKD patients who were either on hemodialysis (Study AKB-6548-CI-0011) or CKD patients who were not on dialysis (Studies AKB-6548-CI-0005 and AKB-6548-CI-0007)
 
 
The target enrollment will be approximately 48 subjects for the study with 12 subjects enrolled in each of the 4 treatment groups.
 
The study is powered based on a comparison of the highest dose vadadustat group (600 mg daily) and the placebo group.
 
Based on the results from Study AKB-6548-CI-0005 that was conducted in the United States and evaluated vadadustat in patients with anemia secondary to NDD-CKD, it is assumed that the expected mean Hb changes from pre-treatment to Week 6 will be approximately 0 mg/dL for the placebo group and 1.35 g/dL for the highest dose vadadustat group (600 mg daily).
 
Based on the results from Study AKB-6548-CI-0011 that was conducted in the United States and evaluated vadadustat in patients with anemia secondary to DD-CKD, it is assumed that the common Hb standard deviation will be 0.9 g/dL across treatment groups. In addition, a dropout rate of 10% is assumed. With these assumptions, the study with n=12 subjects per group will have >85% power to detect the difference between treatment group and control group, at 2-sided alpha of 0.05.
 
In addition to the final analysis which will take place when all subjects have completed the study and will include all data collected, the 6-week efficacy and safety data will be


	
summarized for administrative planning purposes after the last patient completes the primary efficacy period (Week 6). The preliminary analysis will be performed and interpreted by sponsor and CRO study team personnel. Subjects and sites will not be unblinded to treatment allocation. Individuals from the sponsor and CRO study teams who are unblinded for the development and reporting of the preliminary analysis will not be involved in the conduct of the study after the preliminary analysis. As the study conduct and final analysis will not be modified by this analysis, no alpha adjustment is proposed. It is expected that this 6week data will be identical for the preliminary administrative analysis and the final analysis of the complete dataset. Any changes between the preliminary analysis and the final analysis will be documented.

--	---

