### 9.3.2 Laboratory Evaluations

Samples for laboratory assays will be sent to a central laboratory for analysis. Detailed instructions for the collection, processing, and shipment of laboratory samples will be provided by the sponsor and the central laboratory. The investigator is responsible for reviewing laboratory results for clinical significance.

The following laboratory evaluations will be conducted during the study:

- Serum pregnancy tests: Female subjects who are of childbearing potential (ie, are not surgically sterile or postmenopausal) will participate in serum pregnancy tests (to be analyzed by the central lab). The screening pregnancy test results must be available and must be negative for a subject to initiate study drug.
- Note: Additional serum or local urine (if possible) pregnancy tests may be conducted, as determined by the investigator or required by local regulations, to establish the absence of pregnancy during the study. Coagulation tests: Blood sample will be collected to assess the prothrombin time (PT), partial thromboplastin time (PTT), and international normalized ratio (INR).

- Folate and vitamin B12: Blood sample will be collected to assess folate and Vitamin B12 levels.
- CBC: Blood sample will be collected to assess CBC, including Hb, hematocrit, RBC count, mean corpuscular volume, mean corpuscular Hb, mean corpuscular Hb concentration, red cell distribution width, white blood cell count with differential (neutrophils, bands, lymphocytes, monocytes, eosinophils, and basophils), platelets, and automated reticulocyte count (both absolute and percent).

Blood samples for CBC/Hb assessment will be collected with the patient in the supine position and prior to hemodialysis (per the Japanese Society for Dialysis Therapy [JSDT] guidelines). As noted in Appendices

[Appendix A](#) and [Appendix B](#), the following visits will be scheduled for the first hemodialysis of the week:

- For patients not prescribed ESAs: Screening visit 1, screening visit 2, baseline visit/Day 1, Week 6, Week 16
- For patients prescribed ESAs: Screening visit 2, screening visit 3, baseline visit/Day 1, Week 6, Week 16

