4.2 General Presentation Considerations

Pre-treatment Hb is defined as the average of 3 Hb values obtained prior to treatment based on most recently 2 qualifying screening Hb values and the Hb value at the baseline visit (Day 1). 'Pre-treatment' for other variables is defined as the last available pre-treatment assessment. In general, this is the value at the Baseline Visit. 'End of Treatment (EOT)' is defined as the assessment on the EOT form labeled as 'Week 16 Visit', even if other values closer to Day 113 are available. For the analysis purpose, only actual visit will be used and hence EOT will be presented as "Week 16". In the summary table, EOT of early withdrawal will not be counted but only be displayed in the listing for reference purpose. 'Treatment Day' will be calculated relative to start of dosing at Baseline Visit (i.e. Treatment Day = Assessment Date - Baseline Visit Date + 1).

Continuous data will be summarized in terms of the mean, standard deviation (SD), median, minimum, maximum and number of observations, unless otherwise stated. The minimum and maximum will be reported to the same number of decimal places as the raw data recorded in the database. The mean and median will be reported to one more decimal place than the raw data recorded in the database. The SD will be reported to two more decimal places than the raw data recorded in the database. In general, the maximum number of decimal places reported shall be four for any summary statistic.

Categorical data will be summarized in terms of the number of subjects providing data at the relevant time point (n), frequency counts and percentages. Any planned collapsing of categories will be detailed in the SAP text and the data displays.

Percentages will be presented to one decimal place. Percentages will not be presented for zero counts. Percentages will be calculated using n as the denominator. If sample sizes are small, the data displays will show the percentages, but any textual report will describe frequencies only.

Changes from baseline in categorical data will be summarized using shift tables where appropriate.

P-values greater than or equal to 0.001, in general, will be presented to three decimal places. P-values less than 0.001 will be presented as “<0.001”.

Confidence intervals will be presented to one more decimal place than the raw data.

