The number and percentage of subjects above / within / below target range who are maintained within the target range at their previous visit after Week 6 will be provided by treatment group.

The effect of treatment in terms of the proportion of subjects within target Hb level at Week 6 will be analyzed using Fisher's exact test. Three post-hoc pairwise comparison, i.e., placebo vs 150 mg, placebo vs 300 mg, and placebo vs 600 mg, will be done.

A by-subject listing will be provided.

Increase in Hb from pre-treatment average

A summary of the cumulative number and percentage of subjects who achieved a ≥ 1 g/dL increase in Hb from pre-treatment average will be provided by treatment group. In addition, the cumulative proportion of subjects within target range will be displayed graphically from baseline visit to follow up visit by treatment group.

The effect of treatment in terms of the proportion of subjects who achieved a ≥ 1 g/dL increase in Hb from pre-treatment average will be analyzed using Fisher's exact test. Three post-hoc pairwise comparison, i.e., Placebo vs 150 mg, placebo vs 300 mg, and placebo vs 600 mg, will be done.

Hematocrit, RBC count, and reticulocyte count (CBC)

Hematocrit, RBC count, and reticulocyte count (both absolute and percent) will be analyzed as secondary efficacy variables.

The following summaries will be provided:

- A summary of hematocrit, RBC count, and reticulocyte count (both absolute and percent) by treatment group and time point. 1st and 3rd quartiles (Q1, Q3) as well as the mean, SD, median, minimum, maximum and number of observations will be presented.
- A summary of the change (absolute and percent) from baseline in hematocrit, RBC count, and reticulocyte count (both absolute and percent) by treatment group and time point.
- Box plots of absolute changes from baseline in hematocrit, RBC count, and reticulocyte count for each treatment group at each post-treatment time point.

The effect of treatment in terms of the change from baseline to Week 6 in hematocrit and RBC count and reticulocyte count (both absolute and percent) will be analyzed using ANCOVA. The statistical model will assess the main effect of treatment, adjusted for baseline measurement. LS-means for each treatment and their 95% CIs will be presented. Three post-hoc pairwise comparison, i.e., Placebo vs 150 mg, placebo vs 300 mg, and placebo vs 600 mg, will be done. Unadjusted ANOVA will be performed for sensitivity.

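### The Week 6 ANCOVA of hematocrit, RBC count and reticulocyte count adjusts for one pre-dose value although three are collected; adding the screening mean as a second covariate is a cheap, modest gain in precision

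*Protocol*

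**What the plan says.** For hemoglobin, the Protocol Synopsis states that "a pre-treatment average value for Hb is defined as the average of 3 values obtained prior to dosing": the two qualifying screening values and the Day 1 value. Hematocrit, RBC count and reticulocyte count are instead defined as changes from baseline: "Mean change in hematocrit, RBC count, and reticulocyte count from baseline to the end of the primary efficacy period (Week 6".

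SAP 4.2 says that the pre-treatment value "for other variables is defined as the last available pre-treatment assessment. In general, this is the value at the Baseline Visit". SAP 4.7.3 then plans a Week 6 ANCOVA for hematocrit, RBC count and reticulocytes (absolute and percent): "The statistical model will assess the main effect of treatment, adjusted for baseline measurement". It promises LS means with 95% confidence intervals for each arm, three pairwise comparisons with placebo, and an unadjusted ANOVA as sensitivity.

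Protocol 9.3.2 describes the sample: "Blood sample will be collected to assess CBC, including Hb, hematocrit, RBC count" and, further on in the same list, the automated reticulocyte count. Appendices A and B schedule this CBC at both qualifying screening visits and on Day 1: SV1, SV2 and Day 1 for subjects not on ESAs, and SV2, SV3 and Day 1 after washout. Protocol 9.1 and 9.3.2 put all three visits on the first hemodialysis session of the week, with supine, pre-dialysis sampling.

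**The concern.** One tube gives Hb and the other three variables, at the same visits and under the same conditions. Hb uses three of these values; the others use one. The documents give no reason for the difference.

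A single pre-dose value carries measurement and day-to-day noise. As a covariate it therefore predicts the Week 6 value less well than three values could, and the unexplained part stays in the residual variance of every comparison with placebo. With about 11 to 12 subjects per arm, that is worth a look. Week 6 is also the last placebo-controlled time point, because placebo subjects then switch to vadadustat.

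**Working it through.** **Inputs**
- From Protocol 11.2: 12 subjects per group, 10% dropout (12 × 0.9 = 10.8, taken as 11), two-sided alpha 0.05.
- From Protocol 9.3.2 and Appendices A and B: three comparable pre-dose CBC samples per subject.
- Assumed, because the documents give neither: reliability of one value r = 0.6 to 0.8; response heterogeneity t = 0.25 to 0.5 of the between-subject variance.

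**1. The plan's own figure.** There is no power or precision figure for these three variables. The Hb figure in Protocol 11.2 (above 85%; difference 1.35 g/dL, SD 0.9 g/dL) is reproduced: the t-test power is 0.939 with 12 per group, 0.917 with 11 and 0.887 with 10. It is not in question here.

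**2. How much information the extra values hold (closed form).** Set the true-value variance to 1 and the noise variance to w = 1/r − 1. The ANCOVA residual variance is:
- one value: (1 − r) + t + w
- mean of three: (1 − r3) + t + w, with r3 = 1/(1 + w/3)

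For r = 0.7 and t = 0.5: w = 0.429 and r3 = 0.875.
- One value: 0.300 + 0.500 + 0.429 = 1.229.
- Mean of three: 0.125 + 0.500 + 0.429 = 1.054.
- The cut is 14%, and the width ratio is √(1.054/1.229) = 0.926.

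Over the assumed grid the cut is 13% to 18%, so widths are 7% to 9% narrower. This is for the mean of three as one covariate, which is not the model recommended below.

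**3. The recommended model (simulation).** Four arms of 11, change from Day 1 as response. Covariates: Day 1 alone (39 error degrees of freedom) against Day 1 plus the screening mean (38). The table shows the ratio of mean 95% interval widths for a dose-minus-placebo contrast.

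| r | t = 0.25 | t = 0.5 |
|---|---|---|
| 0.6 | 0.925 | 0.942 |
| 0.7 | 0.920 | 0.939 |
| 0.8 | 0.920 | 0.948 |

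Intervals are about 5% to 8% narrower. This is worth 1/0.948² = 1.11 to 1/0.920² = 1.18 times the subjects per arm. The residual variance falls almost as far as in step 2. The difference is the price of the second covariate: one degree of freedom, and chance imbalance between arms in that covariate.

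**4. Stress tests on the same model**
- *Drift after washout.* Subject slopes with SD 0.3 between-subject SDs per week. If the drift stops at Day 1, intervals are about 3% to 5% narrower. If half persists to Week 6, they run from about 1% narrower to about 1% wider.
- *Restricted range.* Entry requires mean screening Hb below 10.0 g/dL. If a variable tracked Hb perfectly and half of those screened qualified, intervals would be about 3% to 5% narrower.

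**5. Why two covariates and not one average.** With serial correlation that decays over time and no measurement noise, the plain mean of three gave standard errors up to 1.04 times those with Day 1 alone. Separate covariates let the data weight recent against older values.

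**The case against.** The strongest case against is that nothing here is wrong. The protocol consistently uses a three-value average for Hb and baseline for the other variables. SAP Amendment 1 (Change#1) moved the listed efficacy variables from pre-treatment to baseline, which suggests a deliberate choice. ANCOVA on one baseline value is valid. SAP 4.7.1.4 describes the secondary variables as supportive, with no labeling claims. The gain rests on assumed reliabilities and can vanish. All of that stands, and it sets the grade.

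It does not answer the narrower point: comparable measurements already in the database are left out of a small-sample model, and including them leaves the endpoint as it is.

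Some stronger readings might be inferred, and the documents do not support them:
- *These are the only secondary laboratory efficacy endpoints with an ANCOVA.* They are not. SAP 4.7.3 also plans one for Hb change from the baseline visit.
- *Hb and hematocrit cannot be compared because they refer to different pre-dose values.* That same secondary Hb analysis puts Hb on the single baseline value, and the change proposed here would not alter either reference.
- *Published dose-versus-placebo intervals will be too wide.* SAP 4.7.3 promises intervals for the arm LS means, and pairwise comparisons; it does not explicitly promise intervals for the differences. The same residual variance enters all of them.

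A practical objection also has force: a qualifying screening value is defined only for Hb, so the covariate needs its own definition and a rule for a missing value.

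**Conclusion.** The point holds as a minor, inexpensive improvement in precision. The planned Week 6 ANCOVA is valid and unbiased, and the primary Hb analysis is untouched.

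On assumed reliability 0.6 to 0.8 and heterogeneity 0.25 to 0.5, with stable pre-dose values, standard errors and pairwise intervals would be about 5% to 8% narrower. The gain falls to about zero, at worst about 1% wider, with strong drift after ESA washout that persists to Week 6. One reliability range was applied to all three variables; reticulocytes, and subjects still drifting after a washout as short as two weeks, are where the gain is least certain. A reader might take the planned model for a source of bias or of a wrong error rate; it is neither.

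**What to change.** In SAP 4.7.3, for hematocrit, RBC count and reticulocyte count (absolute and percent):
- Keep change from baseline to Week 6 as the response.
- Enter two covariates: the Day 1 value, and the mean of the same variable at the two visits that supplied the qualifying screening Hb values. Defining it by those visits also settles retests.
- If only one of the two screening values is available, use that one, as SAP 4.7.2 does for Hb.
- Report the Day-1-only model as sensitivity.

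The cost is a short addition to the SAP, one error degree of freedom and one extra model run per variable. No new data are needed. The text should be fixed before the unblinding for the preliminary 6-week analysis.
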